Study 2 is designed to complement Study 1 in providing additional support for the hypothesis that burst suppression is an important mechanism for antidepressant treatment effects of anesthesia in moderate to severe depression. If Study 1 demonstrates that more participants receiving High ISO/BS+ undergo remission than those receiving Low ISO/BS-, this could be interpreted as a dose response effect for isoflurane that is not specifically a result of burst suppression. Demonstrating that a different anesthetic administered at doses producing 80% burst suppression for 10 treatment session is also effective in producing depression remission would add support for the hypothesis that the underlying mechanism is burst suppression. Therefore, Study 2 will be an open-label trial to provide preliminary data that propofol, an intravenous anesthetic with a favorable safety profile, administered for 10 treatment sessions at levels to induce 80% burst suppression, also is effective in producing depression remission in 50% or more of the pilot sample of 10 depressed participants.

Aim 4. To determine whether propofol anesthesia at a level to produce 80% EEG burst suppression is effective in producing remission of depressive symptoms. We hypothesize that

the majority of depressed participants (n=10) receiving 10 treatments of propofol anesthesia will achieve remission of symptoms by treatment end.

Aim 5. Preliminary data on neural and immune pathways that are differentially affected by the 2 treatments and associated with antidepressant effects will be explored using full transcriptome leukocyte gene expression (RNA Seq).

Aim 6. To measure the central neurochemical effects of propofol treatment, we will quantify neurotransmitter levels (GABA and glutamate) using magnetic resonance spectroscopy.

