### **Subject Withdrawal and Study Completion**

Subject compliance will be monitored throughout the trial by study staff. If any contraindications to the study are identified, participants may be withdrawn by the investigators. Participants can be withdrawn at any point if the investigators feel it is in the participant's best interest or in the interest of study integrity. No information will be collected from withdrawn participants unless it is related to a continuing AE or SAE.

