High ISO/BS+ (n=15): The High ISO/BS+ group will receive isoflurane at the same level used in our previous study, with the initial vaporizer setting at 4%. End-tidal isoflurane concentration will be measured continually and is the best measure of alveolar concentration. Alveolar concentration will approximate effect site concentration. In this study we are directly measuring isoflurane effect on CNS electrical activity via the EEG (BIS) and burst suppression ratio is continually calculated and displayed. As the end tidal isoflurane concentration increases and the burst-suppression ratio increases, the vaporizer setting will be decreased. The goal is a burst-suppression ratio of 80%. Some burst suppression is seen at concentrations as low as 1MAC of isoflurane (1.15%) and most patients will achieve 80% BSR at 2 MAC or less (2.3%). These doses are well within the normal range for isoflurane use and are achieved on a daily basis in the O.R.s at this institution. As in the prior study by [name] et al , this condition of isoflurane-induced electrical quiescence will be maintained for 15 minutes.

Low ISO/BS- (n=15): ISO concentration will be titrated to maintain unconsciousness with burst suppression of  $\leq 20\%$ . This condition will be maintained for 15 minutes.

**5.1.2 Study 2. Open-Label Propofol Treatment:** Participants in the propofol treatment group will receive an induction dose of 2-3 mg/kg IV bolus, followed by propofol infusion at 100-400 mcg/kg/min. Additional boluses (0.5-2 mg/kg), administered every 2-3 minutes, may be necessary to achieve and maintain 80% burst suppression on EEG. At the end of the treatment, propofol administration will be discontinued and the participant will be allowed to awaken. Similar means of propofol induced burst-suppression is commonly and safely administered during neurosurgical procedures. Monitoring and supportive treatment will be consistent with clinical standards outlined by the American Society of Anesthesiologists as discussed above for participants in the main study. We will enroll up to 10 participants in the propofol pilot study.

**5.1.3 Anesthetic Emergence (All Treatments):** Emergence from isoflurane anesthesia into consciousness will be facilitated by the Aneclear device (QED 100™) according to FDA approved guidelines and as routinely used in the University of Utah operating rooms.

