### **6.3 Safety and Efficacy Monitoring**

All serious adverse events will be reported within 5 days to the Data and Safety Monitoring Board (DSMB) and IRB by the Principal Investigator or study coordinators. These would include life-threatening cardiac arrhythmias, respiratory arrest, myocardial infarction, stroke, and death. Moderate adverse events including worsening of depressive symptoms will be reported to the DSMB. An interim data analysis will be performed at the midpoint of this pilot investigation, after data is obtained from 5 participants in each of the treatment conditions. The study will be terminated if significantly greater negative outcomes are associated with either isoflurane treatment or propofol treatment.

Prior to each treatment, participants will fill out the QIDS-SR. HRSD-24 will be obtained at baseline, before treatment 6, and after treatment 10. All participants will be assessed before the 6th treatment. If participants in Low ISO/BS- or propofol treatment groups show clinical deterioration (defined by 2 consecutive QIDS scores below baseline OR a decrease in HRSD-24 before the 6th treatment), they will be offered treatment at the 80% burst suppression level (High ISO/BS+) as it has proven effective in reducing depression or ECT as the standard of care treatment. Participants in High ISO/BS+ treatment who show clinical deterioration, as defined above, will be offered ECT. All serious adverse events will be reported within 5 days to the DSMB by the Principal Investigator or study coordinators. The DSMB will also be notified within 10 business days if a study participant is showing signs of clinical deterioration (defined as 2 consecutive QIDS scores below baseline OR HRSD-24 below baseline). Progress reports will be submitted every 6 months. If a participant has a serious reaction to anesthesia, they will be withdrawn from the study.

As exploratory biomarkers, we will evaluate whether quantitative cortical EEG changes early in treatment (obtained from dual lead BIS data in each treatment session) are associated with subsequent remission in depressive symptoms.

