## **7. Statistical Considerations**

Statistical analyses will employ a statistical mediation model framework. Any participant missing necessary information will be excluded from statistical analysis. Only participants with usable data will be included in the analyses. If the original statistical plan becomes infeasible, the original plan and the modifications made will be reported.

**7.1 Aim 1.** To determine if significantly more depressed participants randomized to receive 10 treatments of High ISO/BS+ will show a positive treatment response (defined as 50% reduction in depression scores) or achieve full remission of symptoms by treatment end compared to those in the Low ISO/BS-group, odds of treatment response and remission will be compared between groups using logistic regression analysis with positive response at treatment end (yes/no) as the dependent variable, and treatment group (High ISO/BS+ vs Low ISO/BS-) as the independent variable. Positive treatment response is defined as 50% reduction in depression scores, and remission will be defined as a score of 0-10 on the HRSD-24 scale.

Covariates will include baseline depression severity and possibly other baseline demographic and clinical measures as needed.

**7.2 Aims 2 and 5.** Using RNA SEQ methods, we will also explore whether participants who respond to treatment show blood-based changes in gene expression of neural and immune pathways previously associated with refractory depression or suicidality by our group or others. A t-test or non-parametric Wilcoxon test will be used, as appropriate. Change from baseline to end of treatment in gene expression levels will be correlated with change from baseline to end of treatment in HRSD-24.

**7.3 Aim 4.** In the open-label trial of propofol, initial evidence of efficacy will be defined by the percent of participants who show at least a 20% reduction in both HRSD and QIDS scores (initial improvement, as employed in the STAR D investigation) and who are propofol/BS+ responders (defined as 50% or more reduction in both HRSD-24 and QIDS scores). Secondary evidence of efficacy will be defined by comparing the percent of participants who are responders to propofol/BS+ vs. to the Low ISO/BS- control condition in the randomized trial.

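### Aim 4 asks about remission on propofol, but Section 7.3, its only analysis, measures 20% and 50% score reductions and never counts remission

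*Combined protocol and SAP*

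**What the plan says.** **The aim.** Section 2.2 sets two remission targets for the propofol pilot. The rationale looks for evidence that propofol "also is effective in producing depression remission in 50% or more of the pilot sample of 10 depressed participants". The Aim 4 hypothesis is that "the majority of depressed participants (n=10) receiving 10 treatments of propofol anesthesia will achieve remission of symptoms by treatment end".

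**The analysis.** Section 7.3 is the only subsection of Section 7 given to Aim 4. It says that "initial evidence of efficacy will be defined by the percent of participants who show at least a 20% reduction in both HRSD and QIDS" scores, "and who are propofol/BS+ responders (defined as 50% or more reduction in both HRSD-24 and QIDS scores". Its secondary evidence is the responder percentage on propofol against that on Low ISO/BS-. Remission is not mentioned.

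**Remission elsewhere.** Section 2.1 (Aim 1) requires HRSD-24 of 0-10 together with QIDS-SR of 0-5. Section 7.1 requires HRSD-24 of 0-10 only. Both stand under Aim 1.

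**Who is counted.** Section 5.1.2: "We will enroll up to 10 participants in the propofol pilot study". Section 7, opening paragraph: "Any participant missing necessary information will be excluded from statistical analysis". Subject Withdrawal and Study Completion: "No information will be collected from withdrawn participants unless it is related to a continuing AE or SAE". Section 6.3 offers High ISO/BS+ or ECT to propofol participants who meet its definition of clinical deterioration.

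**The concern.** The protocol gives propofol remission a specific job. Section 2.2 explains that a Study 1 difference could be read as an isoflurane dose effect, and that remission under a second agent at the same burst suppression level would support burst suppression as the mechanism. If Section 7.3 is followed, the report will give two improvement percentages and a responder comparison, and nobody will know from it how many participants remitted. A favourable response rate could then be read as support for a remission hypothesis that was never examined.

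Inserting the word remission into Section 7.3 would not be enough. The target, the definition and the denominator are each unsettled, and with at most 10 participants each can change the conclusion. The denominator matters most. People who withdraw without an end score drop out of the analysis, and that can raise the reported rate.

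**Working it through.** The plan derives no sample size or precision for Aim 4, so there is no figure to reproduce. The checks below use the plan's own cut-offs, plus assumed remission rates and dropout counts that are labelled as such.

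**1. Do the Section 7.3 endpoints imply remission?** Inputs: entry HRSD above 18, so at least 19 (Section 4.1); HRSD-24 remission 0-10 (Sections 2.1 and 7.1).

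- 20% fall from 19: 0.8 × 19 = 15.2, not remission.
- 50% fall from 22: 0.5 × 22 = 11, not remission. From 30 it is 15.
- Converse: 19 to 10 is in the HRSD remission range, but (19 − 10)/19 = 47.4%, so it is not a response.

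The final words of the Section 7.3 definition are also unclear. Anyone with a 50% fall on both scales also has a 20% fall, so if the two conditions are read jointly the 20% threshold does nothing.

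**2. How far apart were response and remission before?** Section 3, earlier open-label isoflurane study, n = 8: response 0.75 × 8 = 6 (on HRSD); remission 0.50 × 8 = 4 (scale not stated). The gap is two people in eight.

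**3. Do the two targets differ?** P(X ≥ r) for X binomial(n, p), where n is the number analysed and p an assumed true remission rate:

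| n | r for at least half | r for a majority | p = 0.50 | p = 0.30 |
|---|---|---|---|---|
| 10 | 5 | 6 | 0.623 vs 0.377 | 0.150 vs 0.047 |
| 9 | 5 | 5 | 0.500 for both | 0.099 for both |
| 8 | 4 | 5 | 0.637 vs 0.363 | 0.194 vs 0.058 |

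**4. What does the denominator do?** Assume 10 start, 4 remit, and those without an end score are not in remission.

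| No end score | Rate among those with scores | Rate among starters |
|---|---|---|
| 0 | 4/10 = 40% | 40% |
| 1 | 4/9 = 44.4% | 40% |
| 2 | 4/8 = 50% | 40% |
| 3 | 4/7 = 57.1% | 40% |

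Exact (Clopper-Pearson) 95% intervals: 4/8, 15.7% to 84.3%; 4/10, 12.2% to 73.8%. With two scores missing, the completer rate reaches the at-least-half target and the starter rate does not. With three missing, it also exceeds a majority.

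**5. When is treatment end on QIDS?** Section 5.3.2 collects QIDS before each treatment, and the Schedule of Activities shows none at Post Tx. The last one before monthly follow-up therefore precedes treatment 10, whereas HRSD-24 is taken after it. Every two-scale measure, including those now in Section 7.3, depends on how this is settled.

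**The case against.** The best defence is that two-scale response nearly contains two-scale remission. With HRSD of at least 19 and QIDS of at least 11 at entry, the only two-scale remission that is not a 50% response has HRSD going from exactly 19 to exactly 10. On QIDS there is no exception, since 11 to 5 is already a 54.5% fall. So a low responder rate would count against Aim 4. That is true, but a high rate could not confirm it, and the bound fails under the HRSD-only definition in Section 7.1.

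Second, a target and an intended sample of 10 do appear in Section 2.2, and Section 7 has a general analysis-set rule. That is also true. Neither is carried into Section 7.3 for remission, however; the targets disagree with each other, and the general rule is the one that can inflate the rate.

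Third, the illustrations are chosen near the boundary. With 10 analysed, the targets conflict only at exactly 5/10, which has probability 0.246 at a true rate of 50%, 0.103 at 30% or 70%, and 0.026 at 20%. The documents give no dropout figure. This limits the size of the target and denominator points and leaves the missing endpoint untouched.

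Finally, this is an open-label pilot meant to yield preliminary data, and the response percentages do serve that wider purpose. That bears on how serious the point is. The stated hypothesis still goes unanswered.

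**Conclusion.** The concern holds. Section 7.3 answers a different question from the one Aim 4 asks, and no other section supplies a remission analysis for propofol. This rests on reading the two sections side by side and needs no assumption. The sizes do need assumptions. The choice of target moves the chance of success from 0.62 to 0.38 with 10 analysed at a true rate of 50%, and by less at other rates. The completer rule turns 40% into 50% if 4 of 10 remit and 2 lack end scores. The point should be corrected before analysis. It does not affect the randomised comparison in Aim 1, except that the remission definition must be reconciled across both studies.

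**What to change.** Amend Section 7.3 as follows.

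- **Main result:** number and proportion of propofol participants in remission at treatment end, with an exact 95% confidence interval.
- **Denominator:** everyone who started propofol, with a missing end-of-treatment score counted as not in remission. Give completers only as a sensitivity result. State how a participant who switches treatment under Section 6.3 is counted.
- **Definition and target:** one remission definition, reconciling Sections 2.1 and 7.1 and expressly covering Study 2. Set one target, stated as a proportion because enrolment may fall short of 10.
- **Timing:** for every two-scale measure, name the QIDS that counts as treatment end.
- **Supportive results:** the 20% and 50% reductions as two separate percentages.
- **Comparison with Low ISO/BS-:** the same responder definition in both groups, labelled non-randomised and descriptive, since participants choose their study (Section 4.3).

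The cost is SAP wording. HRSD-24 is already collected after treatment 10, and counting missing scores as not in remission needs no new data. A QIDS at Post Tx, if chosen, adds one self-report form. The drawback is that the reported pilot result may look less favourable.

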### **4.3 Study Recruitment Procedures**

Potential participants will be recruited to the study through one of three ways: chart review, referral, or direct enrollment.

Recruitment via chart review: Potential participants will first be identified through review of medical records by trained study staff; specifically, examination of the records of patients who have been scheduled for an ECT consultation at the University Neuropsychological Institute (UNI). Participants who may be eligible for screening will be told about the study toward the end of their consultation. Interested patients will be screened and consented either right after the ECT consultation or during a separate appointment.

Recruitment via referral: Physicians from the Department of Psychiatry who have been informed of this study may also refer patients for screening. Patients who are referred will be contacted by study staff to arrange for screening and consent.

Direct enrollment: Psychiatrists listed on the study protocol may identify potential research volunteers during their ECT consultations. These patients will be informed of the research, and if interested, will be screened and consented.

Participants will be informed that there are two study options and that they will be able to decide which one they will participate in. For the isoflurane study, we will explain that some preliminary evidence shows that high dose isoflurane is effective in reducing depression symptoms. However, if the isoflurane study is chosen, there is a 50:50 chance of being in the low dose isoflurane treatment, and the individual will not know what treatment group (high vs low dose) they are in. We do not know whether low dose isoflurane will reduce depression symptoms. For the propofol study, we will explain that this arm of the study is open-label, meaning they will know they are receiving propofol treatment at a dose that produces burst suppression. We will also inform participants that we do not know if propofol treatment will be effective in reducing symptoms of depression.

We hope to enroll at least 1 participant per week and have a maximum capacity of 4 participants per week with a total of 45 participants enrolled in the study (30 in Study 1 and 10 in Study 2).

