#### **4.5 Study Visits**

**Screening:** Patients who have been referred or have volunteered for the study will be screened in person or by phone to verify that inclusion and exclusion criteria have been met.

**Consent procedures:** Each patient will be given a full verbal explanation of the study procedures, including risks, benefits, and alternatives, and will be given a copy of the approved written consent form. The patients will be given the opportunity to review the consent form and to discuss any questions or concerns with their own psychiatrist, our study investigators, or others if necessary prior to beginning study treatment procedures.

**Baseline:** Prior to the first treatment, depression severity will be assessed via a psychiatric interview, including completion of the HRSD-24 and MoCA, which will also verify inclusion and exclusion criteria. Immediately before treatment 1, the participant will complete the QIDS and a blood sample will be obtained from the IV line.

**Randomization (Study 1 only):** Participants who meet study criteria will be randomly assigned in blocks of 4 to either high or low dose isoflurane (High ISO/BS+ vs. Low ISO/BS-). We anticipate up to 15 participants in each arm; this sample size was defined by our prior study in which 8 participants were adequate to show significant antidepressant effects.

**Leukocyte Gene Expression:** Although our study is designed with EEG burst suppression as our primary target mechanism, we acknowledge that its effects must be mediated via specific neural pathways. Thus, we will explore possible neural and immune pathways associated with the antidepressant effects of deep anesthesia. Changes in full transcriptome leukocyte gene expression from pre- to post-treatment will be assessed from blood samples drawn before the first treatment and within 48 hours of the final (10th) treatment. In particular, we will examine the possible role of GABA-ergic and ATP-responsive ion channel pathways as well as other putative depression- or suicidality-linked neuroimmune pathways. We will also evaluate other ATP-responsive ion channels (purinergic, acid sensing and transient vanilloid receptor) or other

genes including IL-10 and other cytokines, SAT1, PTEN, MARCKS and MAP3K3 previously associated with refractory depression or suicidality by our group and others. [42918](#)

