## **5.3 Clinical Assessments**

**5.3.1 Primary Response Assessments:** The primary outcome measure is change in depressive symptoms assessed by the Hamilton Rating Scale for Depression (HRSD-24), which is the most widely used method of evaluating the effectiveness of treatments to relieve depression. HRSD-24 will be administered as part of a clinical interview by blinded investigators prior to beginning the treatments, then repeated before treatment #6 and at the end of treatments.

**5.3.2 Secondary Response Assessments to be acquired before each treatment:** Also as standard of care for patients receiving ECT, the participant will fill out the Quick Inventory of Depressive Symptomatology (QIDS-SR) which is a patient self-report measure of depressive symptoms prior to each treatment session. QIDS scores will also be used as a safety measure. If 2 consecutive QIDS scores indicate worsening of depressive symptoms, below pre-treatment values, the study participant will meet with one of the study Psychiatrists to discuss treatment alternatives. The Montreal Cognitive Assessment (MoCA), Generalized Anxiety Disorder scale (GAD-7), and Work and Social Adjustment Scale (WSAS) will be administered prior to beginning the treatments, then repeated before treatment #6, and 48-72 hours post treatment #10.

**5.3.3 Follow-up Assessments to be acquired monthly for up to 6-months post treatment period:** Follow-up assessments will include QIDS-SR, WSAS, and an opened ended question about the participant's experience during the study. Follow-up assessments will be administered over the phone or by email with a link to an electronic survey housed on REDCap (a secure online database). A voicemail may be left (with prior permission) regarding the follow-up assessments.

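### Section 7.3 counts a non-randomised comparison of open-label propofol with blinded Low ISO/BS- as evidence of efficacy, a claim that this design cannot support

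*Combined protocol and SAP*

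**What the plan says.** Section 7.3 judges propofol in two stages. The first uses percentages within the propofol group alone: an early-improvement criterion, and response, which requires a halving of both HRSD-24 and QIDS. The second brings in an arm of Study 1: "Secondary evidence of efficacy will be defined by comparing the percent of participants who are responders to propofol/BS+ vs. to the Low ISO/BS- control condition". Section 7.3 names no test, significance level, covariate or caveat for this comparison. The only covariate statement sits under Section 7.1, for Aim 1.

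Other sections show how the two groups arise and how they are assessed:

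- **Allocation.** Section 4.3: "Participants will be informed that there are two study options and that they will be able to decide which one they will participate in". Section 4.5 confines randomisation to Study 1.
- **Participant knowledge.** Under Section 4.3, propofol participants are told that "they will know they are receiving propofol treatment at a dose that produces burst suppression". In the isoflurane study, "the individual will not know what treatment group (high vs low dose) they are in".
- **Outcome assessment.** Section 5.3.1: "HRSD-24 will be administered as part of a clinical interview by blinded investigators". Section 5.3.2 describes QIDS as "a patient self-report measure of depressive symptoms".
- **Study 1 response.** Section 7.1: "Positive treatment response is defined as 50% reduction in depression scores", with no scale named.

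Section 2.2 presents Study 2 as a small open-label pilot that yields preliminary data. It ties support for the burst-suppression mechanism to remission in at least half of 10 propofol participants.

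**The concern.** The Low ISO/BS- arm is a valid control for High ISO/BS+, because those two arms are randomised against each other and share a blind. Neither protection carries over when the arm is set against propofol. People who choose an open-label study may differ in prognosis from people who accept a 50:50 randomisation, and knowing the treatment may change what they report. Section 7.3 nevertheless lets the difference in response count towards efficacy.

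What is at stake is one pre-specified supportive claim for propofol. If the rule is followed as written, a difference produced by selection or expectation would be credited to the drug. The same forces acting the other way could hide a real effect. The randomised comparison in Study 1 is not affected.

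**Working it through.** The documents give no effect size, test or power for this comparison, so there is no figure of the plan's own to reproduce. The check sets the sections side by side and then gauges how easily a non-drug shift could produce a difference.

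**1. What the groups share.** The studies run concurrently (Section 4), use the same eligibility criteria (Sections 4.1 and 4.2), give 10 treatments over 3 weeks in the same procedure room (Section 5.1) and follow one assessment schedule (Section 1). HRSD-24 raters are described as blinded (Section 5.3.1).

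**2. What still differs.**

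| Feature | Propofol | Low ISO/BS- |
|---|---|---|
| Entry to study | Participant's choice | Participant's choice of Study 1, then randomised to dose |
| Knows treatment | Yes | No; told of a 50:50 chance of low dose |
| Agent | Propofol | Isoflurane |
| Burst suppression | 80% target | 20% or less |
| Size | Up to 10 | 15 |

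Rows one and two are sources of bias. Rows three and four are a separate problem. Agent and burst-suppression level change together, and no propofol group without burst suppression exists. Even an unbiased difference could not be divided between drug and mechanism.

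**3. How easily a difference could arise.** Let p be the Low ISO/BS- response rate and s a non-drug shift in the propofol rate. Suppose propofol has no effect of its own relative to Low ISO/BS-. With a responders of 10 and b of 15, the chance that propofol shows the higher percentage is

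sum over all (a, b) with a/10 > b/15 of Bin(a; 10, p + s) × Bin(b; 15, p).

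The last column sums the same product over the tables where a two-sided Fisher exact test gives p ≤ 0.05. The rates (p = 20%, 30%, 40%), the shifts, the test and its level are all assumptions. Ranges run across the three values of p.

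| Shift s | Propofol percentage higher | Fisher p ≤ 0.05 |
|---|---|---|
| 0 points | 45% to 46% | 1.4% to 3.6% |
| 10 points | 66% to 67% | 4.9% to 6.4% |
| 20 points | 82% to 84% | 13% to 14% |
| 30 points | 92% to 93% | 28% |

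Because Section 7.3 only compares percentages, the middle column is the more relevant one.

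**4. Bias and effect look the same.** A true effect that gives 50% against 20% reaches Fisher p ≤ 0.05 in 28% of trials. A 30-point non-drug shift on a 20% base gives exactly the same pair of rates, and so the same 28%. In the other direction, a real 20-point gain offset by a 20-point unfavourable shift returns to the first row: propofol looks better in 45% to 46% of trials. Nothing in the comparison separates these cases.

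**The case against.** The case for leaving the sentence alone has substance. The comparison is labelled secondary, follows the single-arm results, and belongs to a declared pilot. A concurrent control with shared eligibility and schedule is better than a historical one. Blinded HRSD-24 rating limits rater bias. If response must be met on both scales, an inflated QIDS alone cannot make a responder. Section 7.3 plans no formal test, so the last column of the table describes something that the plan does not contain. All of this stands and lowers the weight of the point. It does not remove self-selection or the participant's own expectation, which can also colour answers in a blinded interview. Nor does it separate agent from burst suppression.

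A reader might infer three stronger things that the documents do not support.

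- **That the mechanism conclusion rests on this contrast.** Section 2.2 rests it mainly on the single-arm remission rate. The contrast in Section 7.3 uses response, a different outcome.
- **That the bias favours propofol by some stated amount.** Section 4.3 also tells participants that there is preliminary evidence for high-dose isoflurane and that propofol's effect is unknown. Those seeking a treatment with evidence behind it could choose Study 1, and hopes for propofol could be lower.
- **That the two groups are held to different responder rules.** With 50% response on each scale and kappa k between scales, two-scale response is 0.25 + 0.25k: 35% at k = 0.4 and 45% at k = 0.8, which is 5 to 15 points below 50%. That gap needs a one-scale rule for Low ISO/BS-, which no section states. Section 7.3 defines responders on both scales and then uses the same word for both groups, so one definition is the natural reading. Stating it is a clarification.

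**Conclusion.** The point holds as a limit on what may be concluded. A difference in response between propofol and Low ISO/BS- cannot be attributed to propofol efficacy or to burst suppression. Participants chose their study, only one group knew its treatment, one of the two scales is self-reported, and agent and burst-suppression level differ together. This follows from the design and needs no numerical assumption.

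The direction and size of any bias cannot be determined from the documents. The percentages above show only what an assumed shift would do with 10 and 15 participants; they do not estimate the bias in this trial. The consequence is confined to one secondary claim, but it is a pre-specified efficacy claim with no caveat, and it should be changed.

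**What to change.** In Section 7.3, replace the closing sentence on secondary evidence with a descriptive, hypothesis-generating display that:

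- shows the propofol and Low ISO/BS- response rates, each with an exact confidence interval, and the two groups' baseline characteristics side by side;
- states that the groups differ by self-selection, blinding and agent, and that no efficacy or mechanism claim rests on the contrast;
- states that the two-scale responder definition of Section 7.3 (50% or more on both HRSD-24 and QIDS, at the same visit) applies to both groups.

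The assessment point needs naming. Section 1 marks HRSD at the post-treatment visit but QIDS only at visits 1 to 10 and at follow-up. The text should say which QIDS counts, or the sponsor could add that self-report form to the post-treatment visit.

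The cost is the loss of a nominal supportive efficacy claim for propofol. The change itself is one of wording and needs no additional participants; the optional extra QIDS would be the only added data.
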